enrolled and treated with GT0918 since 9/6/2017 as defined in protocol at five dose levels: 100 mg (n = 3), 200 mg (n = 4), 300 mg (n = 4), 400 mg (n = 4) and 500 mg (n = 3) (as to 7/2/2019). All pts progressed more than two lines of therapies with 83.3% (15/18) pts were treated \geq 3rd lines. Out of 6 confirmed AR positive pts, two (33.3%) at 300 mg cohort had finished 17 and 19 cycles individually and continue treatment (as 7/2/19). No DLT was observed and MTD has not been reached. GT0918 related adverse events (AEs) were grade 1 or 2 as per CTCAE v4.03, including fatigue, hypertriglyceridemia, anemia, hypercholesterolemia, increased LDL, nausea, loss of appetite, increased ALT, increase of weight loss, constipation and thrombocytopenia. PK profile analysis showed that in the single-dose study, GT0918 showed a fast absorption profile. In the multiple-dose study, the steady-state serum concentration level of GT0918 and its main metabolite were attained at 21 days. Conclusions: Proxalutamide (GT0918) administrated orally once a day is well tolerated in late-stage pts. No DLT has occurred at maximum dose 500 mg. Pts with AR positive biomarker could have better clinical outcomes with GT0918 treatment. GT0918 and its main metabolite exhibited a nonlinear pharmacokinetic profile over the dose range from 100mg to 500 mg. An expanded/phase Ib in AR positive mBC pts has launched in China to evaluate the anti-tumor activity and safety of GT0918. 200 mg and 300 mg were selected for dose expansion.

Drug Interactions

Inhibition Potential Assessment of Proxalutamide on Cytochrome P450 Enzymes in Pooled Human Liver Microsomes

The inhibition of human liver CYPs: CYP1A2, CYP2C9, CYP2C19, CYP2D6, CYP2E1 and CYP3A4/5, was assessed with Proxalutamide at concentrations of 0.2, 0.8, 2, 10, 50, 100 and 200 μ M. The metabolite formation from CYP catalyzed probe substrate metabolism was analyzed with LC-MS/MS. The results showed that Proxalutamide showed no significant inhibition on CYP1A2 and CYP2E1, weak inhibition on CYP2D6, CYP2C9, CYP2C19 and CYP3A (midazolam), but marked inhibition on CYP3A4 (testosterone).

The results indicate that there is an inhibitory effect of Proxalutamide on CYP3A4 in vitro and the corresponding in vivo drug interaction potential needs to be further investigated.

***No interaction has been reported between Proxalutamide, nitazoxanide, and azithromycin.**

Table 1.2.3: Inhibitory Effect of Proxalutamide on CYP450 Enzymes

CYP450s	Probe substrate	Characterized Metabolic Pathway	Characterized Metabolite	IC ₅₀ (μM)
CYP1A2	Phenacetin	Deethylation	Acetaminophen	>200
CYP2C9	Tolbutamide	Hydroxylation	4-Hydroxy-Tolbutamide	8
CYP2C19	Omeprazole	Hydroxylation	5-Hydroxy- Omeprazole	8
CYP2D6	Dextromethorphan	Demethylation	Dextrorphan	5
CYP3A4	Midazolam	Hydroxylation	1-Hydroxy-Midazolam	56
CYP3A4	Testosterone	Hydroxylation	6β-Testosterone	1
CYP2E1	Chlorzoxazone	Hydroxylation	6-Hydroxy-Chlorzoxazone	>200

Evaluation of Cytochrome P450 Induction Potential of Proxalutamide in Human Hepatocytes

Proxalutamide was evaluated for induction of drug metabolizing enzymes in primary human hepatocytes. No inductive effects on CYP1A2 and CYP3A4 were observed in the level of enzymatic activity.

Table 10: Effect of Proxalutamide on the Enzyme Activity of CYP1A2

	Activity of CYP1A2 (%)			Mean	SD	Activity compared to positive control (%)
Negative control	109	82.4	108	100	15.2	NA
Positive control	1174	1246	1207	1209	36.3	100
Proxalutamide 1 μM	98.9	98.2	95.6	97.6	1.74	<40
Proxalutamide 10 μM	92.3	98.9	99.6	96.9	4.01	<40

Table 11: Effect of PROXALUTAMIDE on the Enzyme Activity of CYP3A4

Control	Activity of CYP3A4(%)			Mean	SD	Activity compared to positive control(%)
Negative control	97.3	103	99.6	100	2.97	NA
Positive control	805	976	825	869	93.4	100
Proxalutamide 1 μM	24.2	26.0	27.7	26.0	1.73	<40
Proxalutamide 10μM	19.7	21.3	19.4	20.2	1.05	<40

Specific Populations

Pediatric

Proxalutamide pharmacokinetics have not been investigated in subjects younger than 18 years.

Geriatric

No dose adjustment is necessary in the elderly. The pharmacokinetics and pharmacodynamics of Proxalutamide were evaluated in 40 patients with an average age of 70.1 (Study 2, Section 1.1.2.4.).

Gender

Proxalutamide is not indicated for use in women. The planned interventional study will be conducted in men only.

Race

The effect of race on Proxalutamide pharmacokinetics has not been studied.

Renal Impairment

The effect of renal impairment on Proxalutamide pharmacokinetics has not been studied.

Hepatic Impairment

The effect of hepatic impairment on Proxalutamide pharmacokinetics has not been studied.

1.1.3 Prior Pre-clinical Efficacy Data

No prior pre-clinical data exists as to the use of Proxalutamide as a treatment for COVID-19.; however, two studies highlight the possible benefit of the dual anti-androgen activity of Proxalutamide .

Proxalutamide inhibition of androgen binding to AR and AR protein expression

A study by Zhou et al¹⁹ reported that: “GT0918 inhibited the binding of androgen to AR in a dose-dependent manner, and the K_i value of GT0918 (1.4×10^{-8} M) in binding to AR was 3.4-fold lower than that of MDV3100 (4.8×10^{-8} M) (Fig. 1A). It indicated that GT0918 was more potent than MDV3100 in inhibiting the binding of androgen to AR.” Additionally, in cultures of C4-2B cells, “the protein expression of AR was significantly reduced by GT0918”. Data depicting the inhibition androgen binding to AR and the reduced AR protein expression in C4-2B cells is shown below:

[figure not shown]
[figure not shown]

Fig. 1. GT0918 effectively decreases androgen binding to AR. (A) IC₅₀ values for GT0918 and MDV3100 in inhibiting androgen from binding to AR. (B) GT0918 reduces the protein expression of AR in C4-2B cells.

Proxalutamide suppression ACE2 and TMPRSS2 in A549 lung cells

A study by Wu et al²⁰ reported that “In LNCaP and A549 cells, we showed that androgen induced the ACE2 and TMPRSS2 expression, and GT0918 could suppress the ACE2 and TMPRSS2 expression”. The data from the study is depicted in the figure below.

1.1.4 Prior Clinical Efficacy Data

Study 1: Proxalutamide Treatment for Non-Hospitalized COVID-19 Male Patients (NCT04446429)

Proxalutamide has been studied in a prospective clinical trial as a treatment for non-hospitalized COVID-19 male patients. A summary of the study and the results are as follows:

Objective: To determine if the anti-androgen Proxalutamide is an effective treatment for men not-hospitalized due to COVID-19 disease (based on assessment of the clinical status on an 8 point ordinal scale: 8) Death; 7) Hospitalized, on invasive mechanical ventilation or extracorporeal membrane oxygenation (ECMO); 6) Hospitalized, on non-invasive ventilation or high flow oxygen devices; 5) Hospitalized, requiring supplemental oxygen; 4) Hospitalized, not requiring supplemental oxygen - requiring ongoing medical care (COVID-19 related or otherwise); 3) Hospitalized, not requiring supplemental oxygen - no longer requires ongoing medical care; 2) Not hospitalized, limitation on activities and/or requiring home oxygen; 1) Not hospitalized, no limitations on activities)

Design: A double-blinded, randomized, prospective, investigational study of Proxalutamide as a treatment for non-hospitalized COVID-19 male patients (inclusion ordinal scale <3).

Setting: Outpatient centers (Brasilia, Brazil) from October 21 to December 24, 2020.

Participants: Men not hospitalized due to COVID-19 disease (inclusion ordinal scale <3)

Interventions: Proxalutamide 200mg/day, or standard of care for 15 days.

Main Outcome and Measures: Percentage of subjects hospitalized due to COVID-19 [Time Frame: 30 days]

Results: A total of 268 men were included and completed the trial; 134 men were randomized to the Proxalutamide group, and 134 men were randomized to the control group. Data is summarized in Table 1.4.1. A statistically significant difference ($p < 0.001$) in the percentage of subjects hospitalized due to COVID-19 was observed in men taking Proxalutamide compared to the standard of care. The percentage of men hospitalized were 2.2% and 26% in the Proxalutamide and control groups, respectively. No subject receiving Proxalutamide died versus 2 (1.56%) in the control group.

Conclusions and Relevance: Non-hospitalized COVID-19 male patients (inclusion ordinal scale <3) treated with Proxalutamide, had significantly reduced rate of hospitalization compared to men not receiving Proxalutamide.

Trial Registration: NCT04446429

	Control	Proxalutamide
Not Hospitalized	99	131
Hospitalized	35	3
Total	134	134

Table 1.4.1 Clinical outcomes of COVID-19 male patients treated with Proxalutamide compared to standard of care.

Study 2: Proxalutamide Treatment for Non-Hospitalized COVID-19 Female Patients (NCT04446429)

[REDACTED]

[REDACTED]

[REDACTED]

1.1.5 Justification for Dosage

According to a phase I study of Proxalutamide conducted by Zhou et al¹⁹ PK parameters showed that drug exposure increased with dose proportionally from 50 to 300 mg and a saturation was observed between 300mg and 400 mg.

Further, the research team conducting the NCT04446429 study had previously administered to five COVID-19 male patients Proxalutamide at dosages as high as 400mg q.d. These patients did not qualify to be enrolled in the study due to age <50. In the assessment of the research team, these patients were at an imminent threat of hospitalization due to COVID-19. All patients have exhibited shortness of breath, coughing and oxygen saturation $\leq 93\%$. A marked improvement in symptoms was observed 24 hours following administration of 400mg Proxalutamide. None of the imminent were subsequently hospitalized. No treatment related adverse events were observed.

As such, we believe that Proxalutamide 300mg q.d. is likely to provide efficacy in the treatment of hospitalized COVID-19 patients without increasing the rate of treatment related adverse events (none observed in NCT04446429)

1.1.6 Other Data

CONFIDENTIAL

This material is the property of the Applied Biology Inc. Do not disclose or use except as authorized.

The PI has not identified any additional data related to the safety or efficacy of this study.

1.2. Risks/Benefits

This study is designed as a prospective, interventional, placebo controlled, double-blinded, randomized parallel assignment study to assess the efficacy of Proxalutamide as a treatment for hospitalized COVID-19 male and female patients; therefore, we assess below the risks/benefits for the proposed study.

Benefit(s) of the Proposed Clinical Study

To-date no therapy for hospitalized COVID-19 patients has demonstrated significant clinical benefit. Proxalutamide demonstrated clinical efficacy in non-hospitalized COVID-19 patients (NCT04446429). As such, subjects enrolled in this study could potentially benefit from reduced hospitalization time as well as lower risk of experiencing progressively more severe COVID-19 related symptoms. In addition, if Proxalutamide demonstrates clinical efficacy in this study, it is likely to improve the standard of care for hospitalized COVID-19 male and female patients world-wide.

Risk(s) of the Proposed Clinical Study

Treatment with any drug carries risk. Treatment with Proxalutamide carries the risk of the adverse events reported in Phase I clinical trials with Proxalutamide; however, due to the short treatment duration of 14 days, we believe the risk of serious adverse events is lower than described in Phase I studies. Further, during 14 days of dosing 134 subjects with 200mg q.d. of Proxalutamide no drug related adverse events were observed.

1.3. Trial Conduct

This study will be conducted in compliance with the protocol approved by the Institutional Review Board (Ethics Committee), and according to Good Clinical Practice standards. No deviation from the protocol will be implemented without the prior review and approval of the IRB (EC) except where it may be necessary to eliminate an immediate hazard to a research subject. In such case, the deviation will be reported to the IRB (EC) as soon as possible.

1.4. Population

This is a multi-center study to be conducted at hospital sites. This exact protocol will be followed. There will be one or more PIs. The study will be approved by each hospital's Ethics Committee.

The population for this study will be hospitalized COVID-19 patients 18 years or older of any ethnicity. Approximately, 600 (300 males and 300 females) subjects who meet all the eligibility criteria will be enrolled. The estimated time from screening to end of the study for each subject is approximately 28 days.

3.1 Primary Study Endpoints/Secondary Endpoints

Primary Outcome Measure:

1. Treatment efficacy of Proxalutamide relative to placebo arm as assessed by the COVID-19 ordinal scale (defined in Section 5.1) [Time Frame: Day 14]

Secondary Outcome Measures:

1. Treatment efficacy of Proxalutamide relative to placebo arm as assessed by the COVID-19 ordinal scale (defined in Section 5.1) [Time Frame: Day 28]
2. Time to recovery [Time Frame: Day 1 through Day 28]
Recovery is defined as the first day on which the subject satisfies one of the following two categories from the ordinal scale (defined in Section 5.1): 2) Not hospitalized, limitation on activities and/or requiring home oxygen; 1) Not hospitalized, no limitations on activities.
3. Proportion of death [Time Frame: Day 1 through Day 28]
Defined as the number of subjects who have died in each arm divided by the numbers of subjects randomized to the treatment arm
4. Duration of new oxygen use [Time Frame: Day 1 through Day 28]
Duration of new oxygen use measured in days among subjects that did not require oxygen upon randomization.
5. Proportion of subjects testing positive for SARS-CoV-2 [Time Frame: Day 14]
Defined as the proportion of subjects in each arm with a qualitative positive rtPCR SARS-CoV-2 test from upper respiratory tract specimens

3.2 Study Design/Type

This study is designed as a prospective, interventional, placebo controlled, double-blinded, randomized parallel assignment study. The study will have 2 cohorts: men and women and 2 arms:

Arm 1: Subjects administered Proxalutamide 300mg q.d for 14 days + standard of care as determined by the PI at the site

Arm 2: Subjects administered Proxalutamide placebo 300mg q.d for 14 days + standard of care as determined by the PI at the site

Study Environment:

This is a multi-center study to be conducted at multiple hospitals (the sites). This exact protocol will be followed during the study. There will be one or more PIs. The study will be approved by the appropriate Ethics Committees (IRBs). Data collection will be performed at each site by study personnel under the supervision of the PI.

Study Design:

Phase I: Enrollment (within 5 days of admission to hospital):

1. Each subject will be evaluated for the inclusion and exclusion criteria

2. Each subject will undergo a physical examination
3. Each subject (or legally authorized representative) will complete and sign the Informed Consent Form
4. Each subject will be assigned a subject study number
5. Each subject will be randomly assigned to an Arm (Section 3.3)
6. Based on the Arm assignment, each subject will be administered the intervention
7. All information will be recorded in the appropriate CRFs

Phase II: Outcome Assessment at Site (days 1-28):

1. Each subject will be evaluated daily by the PI for the outcomes of this study
2. Based on the Arm assignment, each subject will be administered the intervention
3. The PI will assess each subject for any treatment related adverse events
4. All information will be recorded in the appropriate CRFs

3.3 Randomization

During the enrollment phase (admission to hospital), each subject will be assigned a subject study number. The first subject will be assigned the number 001 and each subject thereafter will be assigned a consecutive number i.e., 002, 003, etc.

In each cohort, subjects will be randomized into 1 of 2 arms in a 1:1 ratio each receiving an interventional treatment.

Arm 1: Subjects administered Proxalutamide 300mg q.d for 14 days + standard of care as determined by the PI at the site

Arm 2: Subjects administered Proxalutamide placebo 300mg q.d for 14 days + standard of care as determined by the PI at the site

In each cohort, each subject will be randomized using an interactive web software: Randomizer.at. The blinding table layout will be a single block. The randomization method used will be permuted blocks of size 4.

This is a blinded study. Neither participants, nor investigators, nor the study team will be aware of treatment assignments prior to the final data base locks at the conclusion of the study (or the interim analysis).

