7.4 Interim Analysis

Interim efficacy and safety data will be made upon recruitment of 50% of the subjects.

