7.5 Termination Criteria

Upon occurrence of any one of the events listed below, the study will terminate or be modified accordingly:

- Completion of the study by a sufficient number of subjects (294 subjects) to reach our confidence level
- Termination of Arm 1: Serious adverse event due to treatment with Proxalutamide
- Substantial evidence of treatment difference between the arms. The study design will be modified to an open-label study.

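### Fixed, published blocks of 4 with masking allowed to lapse at the 50% interim could make up to one third of later allocations certain

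*Combined protocol and SAP*

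**What the plan says.** All references are to the amended protocol covering men and women, unless the final statistical plan is named.

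- **Allocation (3.3).** "In each cohort, subjects will be randomized into 1 of 2 arms in a 1:1 ratio", and "In each cohort, each subject will be randomized using an interactive web software: Randomizer.at". No stratification by site is stated. The method is explicit: "The randomization method used will be permuted blocks of size 4".
- **Masking (3.3).** "Neither participants, nor investigators, nor the study team will be aware of treatment assignments", but only for the period "prior to the final data base locks at the conclusion of the study (or the interim analysis".
- **Interim (7.4).** "Interim efficacy and safety data will be made upon recruitment of 50% of the subjects". The section does not name an independent unmasked group, say who sees assignments, or say that masking continues afterwards.
- **Open-label option (7.5).** On substantial evidence of a difference, "The study design will be modified to an open-label study". Whether randomisation then continues is not stated.
- **Monitor's record (section 11).** The study monitor keeps a separate record of each subject's number, arm, outcomes and laboratory results. Nothing says that the arm is coded or withheld until lock.

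**The concern.** A small fixed block is harmless while past assignments are hidden. Once they are visible, its length tells an observer when one arm must be full. Here the length is printed in a document that every site holds. The masking sentence names an end point that falls when about half the subjects are still to be randomised, and 7.5 and section 11 are two routes by which knowledge of assignments could continue.

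There is room to act on such knowledge. Eligibility spans ordinal scores 3 to 6 (4.1), and enrolment may fall anywhere within 5 days of admission (3.2). If prognosis influenced who was entered next, the Day-14 recovery and 28-day mortality comparisons would be biased at entry. The planned comparisons are unadjusted (7.1; final statistical plan, sections 3 to 5) and could not remove that bias.

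**Working it through.** **Inputs.** Block of 4, 1:1, one list per sex cohort (3.3). 294 per cohort, so 588, rounded in the plan to about 600 (7.2). Interim at 50% (7.4). Placebo recovery 39% (final statistical plan, section 6). Assumed: both cohorts are half recruited at the interim.

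**Plan figures.** The plan gives no predictability figure. Its 294 is used only to count allocations. The formula in 7.2 gives 262.4 if the sum of cubed category probabilities is 0. Reaching 294 with 3.5% dropout needs a sum of about 0.075. Those probabilities are not in the documents, so 294 is neither confirmed nor refuted, and this point does not depend on it.

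**1. Certain allocations, all earlier assignments known.** A block has 6 equally likely orders. The 1st and 2nd places are never certain. The 3rd is certain when the first two match (2 of 6 orders). The 4th is always certain.

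Share certain = (0 + 0 + 1/3 + 1)/4 = 33.3%.

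**2. Best guess (the arm with fewer subjects so far in the block).** The chances of being right by place are 1/2, 2/3, 2/3 and 1.

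Average = (0.500 + 0.667 + 0.667 + 1)/4 = 70.8%, against 50% for an unpredictable list.

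**3. Counts after the interim, if knowledge continues.** Later allocations: 588/2 = 294, or 600/2 = 300. Certain: 294/3 = 98, or 300/3 = 100. Share of all subjects: 98/588 = 1/6. Correct guesses: 0.7083 × 294 = 208, or 0.7083 × 300 = 212.5.

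**4. A one-time look at past assignments.** Only the open block in each cohort is exposed. At 147 enrolled, 147 mod 4 = 3, so 1 allocation is certain. At 150, 150 mod 4 = 2, so the remaining 2 are certain with probability 1/3, or 0.67 expected. At other stopping points the figure lies between 0 and 1 per cohort.

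**5. Illustration of bias, no drug effect.** Suppose every post-interim enrolment is steered: recovery probability is raised by d points when the guess is active drug and lowered by d when it is placebo. With guess rate g = 0.7083,

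spurious difference = 0.5 × 2d × (2g − 1) = 0.4167d.

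With 300 per arm, SE = √(2 × 0.39 × 0.61/300) = 3.98 points.

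| Assumed d | Gap between steered patients | Spurious difference | Type I error (nominal 5%) |
|---|---|---|---|
| 5 | 10 points | 2.1 points | about 8% |
| 10 | 20 points | 4.2 points | about 18% |
| 15 | 30 points | 6.3 points | about 35% |

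A simulation of 20,000 null trials gave 7.8%, 18.2% and 34.5%. Under the one-time look of step 4, even d = 15 gives only about 2/588 × 30 = 0.1 point, and type I error stays at about 5%.

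**6. What varying block sizes would do.** The observer is taken to know the sizes in use but not their order. Certain allocations fall to about 5.6% (sizes 4/6) or 2.0% (4/6/8). Best-guess accuracy falls only to about 69% or 68%. In the d = 10 illustration, type I error falls from 18.2% to 14.9% with sizes 4/6/8.

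**The case against.** A reader might infer that about the last half of allocations can be predicted. The documents do not support that. Half fall after the interim, but at most a third of that half is certain, and only for someone who learns each new assignment as it is made.

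The case against goes further:

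- The masking parenthesis may mean only that assignments are opened for the interim analysis, which is the one-time look of step 4.
- The list is central and per cohort, so a site investigator would also need the order and arms of subjects at other hospitals. Nobody in the documents is shown both to see the whole list and to choose patients.
- The open-label switch needs substantial evidence of a difference, and 7.5 does not say that randomisation continues. If it stops, there is nothing left to predict.
- In a masked, centrally randomised placebo trial, blocks of 4 reveal little, and varying them helps only modestly.
- The final statistical plan was written with the manuscript, so system settings can probably no longer be changed.

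Most of this stands as a limit on size. It does not clear the text. The parenthesis allows the lapse, 7.4 does not restrict it, and section 11 puts arm assignments in the monitor's hands. The baseline-score and site subgroups in the final statistical plan are descriptive. They leave the primary comparison unadjusted and cannot address selection within a score.

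The final statistical plan (section 2) also says that the randomisation scheme was altered at a small remote hospital to control sharing and unblinding. A reader might infer that allocations were in fact predicted. The document does not say so, and the supplement it cites is not available here. It shows only that the research team treated disclosure as a practical risk, and that 3.3 may not describe allocation at that hospital.

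**Conclusion.** The point holds as a weakness in the written rules and is worth a cheap correction. A fixed, published block of 4 is combined with masking that may end for investigators and study team at half recruitment.

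The exposure runs from about one subject per cohort (a single look back) to 98 to 100 certain allocations, one sixth of the total, with 71% of post-interim allocations guessable (continuing knowledge of a whole cohort list). The documents do not say which applies, and a single site would see less than the upper figure.

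The table of type I error should not be read as an estimate for this trial. It rests on continuing knowledge, on steering of every later enrolment, and on a prognostic shift for which the documents give no basis. The masking clause is the main defect. The block size matters because that clause can expose it.

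**What to change.** 1. **3.3, 7.4 and section 11.** Delete the parenthesis that lets masking end at the interim. State that only the analyst preparing the interim sees assignments, and that investigators, monitor and study team stay masked until final lock. Reconcile the monitor's record with this, for example by holding arm codes only. This is the main repair.
2. **3.3.** Use randomly varying block sizes in the existing web system, and keep the sizes out of documents that sites hold.
3. **7.5.** State whether randomisation continues after an open-label switch. If it does, use simple central 1:1 allocation within each sex cohort.
4. **Analysis.** If any subjects were randomised after assignments became known, report the Day-14 comparison stratified by before and after that date, with the before-unmasking estimate as a sensitivity analysis. Stratifying displays a change between periods but does not remove selection within the later one. The before-unmasking estimate is the protected one.

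Cost: a short amendment, a system setting, one extra analysis, and a slightly larger possible arm imbalance, which is small at about 294 per cohort. If enrolment is complete, items 1 to 3 can no longer change the allocation. Item 4 remains possible, together with a statement of who was unmasked and when.
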